7.3.1 Primary endpoint analyses

The primary endpoint absolute change from baseline in maximum reduction in FEV₁ (refer to [Section 5.1.1](#)) is defined as the difference between the maximum reduction in FEV₁ obtained during the treatment challenge and during the baseline challenge.

The primary endpoint will be investigated using descriptive statistics for both trial parts separately and combined.

For the main part of the trial (part II), this primary endpoint will be analysed using a mixed effects model based on the MCS:

$$y_{imj} = \mu + \pi_m + \tau_j + \gamma b_{im} + \gamma' b'_i + s_i + e_{imj},$$

where i = subject 1,..., N, m = period 1,...,4, j = treatment 1,...,4

y_{imj}	CfB in maximum FEV ₁ reduction for the i th subject and the m th period, receiving randomised treatment j
μ	overall intercept,
π_m	m th period effect,
τ_j	j th treatment effect,
b_{im}	baseline value for subject i in period m (period baseline),
γ	associated covariate effect of period baseline,
b'_i	the subject baseline value (mean of period baselines) for subject i,
γ'	associated covariate effect of subject baseline,
s_i	the random effect of subject i,
e_{imj}	the random error associated with subject i who received treatment j in period m.

Proprietary confidential information © 2017 Boehringer Ingelheim International GmbH or one or more of its affiliated companies

The treatment comparisons will be the contrast between active dose and placebo at the endpoint visit. Adjusted means (Least Squares Means) as well as 2-sided 90% Cis will be provided.

Further details will be provided in the TSAP.

7.3.2 Secondary endpoint analyses

The secondary endpoint relative change from baseline in $\text{FEV}_1 \text{ AUC}_{0-\text{tz}}$ (see [Section 5.1.2](#)) is defined as the ratio of $\text{FEV}_1 \text{ AUC}_{0-\text{tz}}$ obtained during the treatment challenge and during the baseline challenge. During each challenge, the area above the curve of the absolute change in FEV_1 from post-diluent value will be calculated from time 0 to tz using the trapezoidal rule (refer to [001-MCG-163](#)). The time tz refers to the last time point before recovery of FEV_1 to within 95% of post-diluent value.

This secondary endpoint will be investigated using descriptive statistics for both trial parts separately and combined.

For the main part of the trial (part II), this secondary endpoint will be analysed using a mixed effects model on the logarithmic scale based on the MCS:

$$y_{imj} = \mu + \pi_m + \tau_j + \gamma b_{im} + \gamma' b'_i + s_i + e_{imj},$$

where i = subject 1,..., N, m = period 1,...,4, j = treatment 1,...,4

y_{imj}	Logarithm of CfB in $\text{FEV}_1 \text{ AUC}_{0-\text{tz}}$ consideration for the i^{th} subject and the m^{th} period, receiving randomised treatment j
μ	overall intercept,
π_m	m^{th} period effect,
τ_j	j^{th} treatment effect,
b_{im}	Logarithm of baseline value for subject i in period m (period baseline),
γ	associated covariate effect of period baseline,
b'_i	Logarithm of the subject baseline value (mean of period baselines) for subject i ,
γ'	associated covariate effect of subject baseline,

Proprietary confidential information © 2017 Boehringer Ingelheim International GmbH or one or more of its affiliated companies

s_i the random effect of subject i,
 e_{imj} the random error associated with subject i who received treatment j
in period m.

To this end, the endpoint will be log-transformed (natural logarithm) prior to fitting the model given above. The difference between the expected means for log(Active)-log(Placebo) will be estimated by the difference in the corresponding adjusted means (Least Squares Means), and a two-sided 90% confidence interval based on the t-distribution will be computed. These quantities will then be back-transformed to the original scale to provide the point estimate and 90% Cis for each endpoint.

The secondary endpoint time to recovery of FEV₁ within 95% of post-diluent value (see [Section 5.1.2](#)) is defined as the time from maximum reduction to last time before recovery to within 95% of pre-MCh challenge during each challenge. The time obtained from the treatment challenge represents the endpoint, while the time obtained from the baseline challenge will be used for the baseline correction in the analysis.

This secondary endpoint will be investigated using descriptive statistics for both trial parts separately and combined, if applicable.

Kaplan-Meier (KM) curves will be plotted for the recovery of FEV₁ within 95% of post-diluent value by treatment irrespective of the period it is administered in, for both trial parts separately as well as combined, if applicable.

For part II of the trial, this endpoint will be analysed using a Cox proportional hazards model as given below based on the MCS. The model includes the treatment effect and an effect for subject baseline. Thereby, the subject baseline is calculated as median of all period baselines per subject. Breslow's method for handling ties will be used.

The hazard function for the ith subject is assumed to be

$$\lambda_i(t) = \lambda_0(t) \cdot \exp\{\beta_1 X_{1i} + \beta_2 X_{2i} + \beta_3 X_{3i}\},$$

where i = 1, ..., N,

$\lambda_0(t)$ is the unspecified, non-negative, baseline hazard function

- $\beta_{1,2,3}$ are the unknown regression coefficients
- X_{1i} represents the treatment group
- X_{2i} represents the subject baseline (median of period baselines)
- X_{3i} represents the period

Proprietary confidential information © 2017 Boehringer Ingelheim International GmbH or one or more of its affiliated companies

For treatment comparisons the hazard ratios of BI 443651 vs. Placebo and asymptotic 95% Wald confidence intervals will be estimated. A hazard ratio of greater than one means that BI 443651 is not inferior to placebo.

Further details will be provided in the TSAP.

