18	Spirometry to be performed pre-MCh challenge, post-diluent and post methacholine dose. Post-methacholine spirometry (FEV ₁ only) timepoints will be relative to the last exhalation of methacholine solution and will be scheduled as single measurements at 30 seconds and 90 seconds, followed by duplicate measurements (FEV1 and FVC) at 5,10, 20, 30,45 minutes, 1.0, 1.25, 1.5, 1.75, 2.0, 2.25, 2.5, 2.75, 3.0, 3.5, 4.0, 4.5, 5.0, 6.0, 7.0 and 8.0 hours
19	Central laboratory: Central laboratory testing (full laboratory screen) will be performed at the screening visit (Visit 1) and on completion of the study (EOT visit / Visit 6). Details of the tests required are provided in Section 5.3.3 .
20	For female subjects: Blood HCG will be performed at screening to confirm eligibility (central laboratory)
21	Electrolytes will be measured prior to start of trial procedures and prior to discharge from the clinic on conclusion of trial procedures at each of the treatment periods (Visits 2 to 5). Initial assessment will be performed by local laboratory. In addition to local testing, a sample for electrolytes will also be sent to the central laboratory.
22	If any significant laboratory test abnormalities are detected, specifically liver function tests, the subject should return to the clinic for repeat testing
23	Spirometry to be performed pre-MCh challenge, post-diluent and post-methacholine dose. Post-methacholine spirometry (FEV ₁) timepoints will be relative to the last exhalation of final methacholine solution and will be scheduled as single measurements at 30 seconds and 90 seconds, followed by duplicate measurements (FEV1 and FVC) at 5, 10, 20, 30, 45 minutes, 1.0, 1.25, 1.5, 1.75, 2.0, 2.25, 2.5, 2.75 and 3.0 hours
24	Must be completed within 30 minutes prior to drug administration
25	FEV ₁ and FVC in triplicate, unless otherwise specified
26	The cumulative times specified in the planned time column are for orientation only. Depending on the actual a.m dosing time at the given day, the procedures and observations related to that a.m dosing (such as pre a.m dose and post a.m dose measurements of the same day) have to be adapted respectively.
27	The end of treatment (EOT) visit should be scheduled no earlier than 14 days after the last dose of study medication. In the event of early discontinuation, an additional earlier visit may be scheduled at investigator discretion.

TABLE OF CONTENTS

CLINICAL TRIAL PROTOCOL.....	1
TITLE PAGE.....	1

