5.1.2 Secondary Endpoint(s)

The following secondary endpoints will be assessed:

- Relative change from baseline in FEV₁ AUC_{0-tz} following bolus MCh challenge
- Time to recovery of FEV₁ to within 95% of post-diluent value

The secondary endpoints will be compared to placebo for each dose level of BI 443651.

For a visualization of the endpoints refer to [Figure 5.1:1](#), a detailed description of the secondary endpoints including statistical analysis is provided in [Section 7](#).

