6.7 BASELINE, TIME WINDOWS AND CALCULATED VISITS

Baseline is defined as the last measurement before first study drug administration in each treatment period.

For endpoints related to methacholine challenge baseline refers to the measurement obtained from the baseline bolus MCh challenge prior to administration of trial medication within each treatment period. The post-diluent value refers to the last measurement before methacholine administration (i.e. timepoint -0:05 relative to methacholine challenge).

Measurements taken after start of administration of trial medication will be considered on-treatment values or follow-up values, based on the definition of the study analysis phases in Section [6.1](#).

Adherence to time windows will be checked at the BRPM/DBLM.

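### Time to recovery is clocked from the nadir and against a reference that contradicts its own name, so a treatment that delayed the nadir could have a later recovery recorded as a shorter one

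*Protocol*

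**What the plan says.** The endpoint lists (Protocol 5.1.2, SAP 5.2) give time to recovery of FEV₁ "to within 95% of post-diluent value". The working definition in Protocol 7.3.2, repeated in SAP 7.5, says that it "is defined as the time from maximum reduction to last time before recovery to within 95% of pre-MCh challenge during each challenge". SAP section 4 lists no change to it.

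Four other places bear on that definition:

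- **Readings.** Flow-chart guidance note 18 (Day 2) reads: "Spirometry to be performed pre-MCh challenge, post-diluent and post methacholine dose". Pre-challenge and post-diluent are listed as separate assessments. SAP 6.7 adds: "The post-diluent value refers to the last measurement before methacholine administration", at −0:05. It does not say that the pre-challenge value is this same reading.
- **Time scale.** In note 18 the post-methacholine "timepoints will be relative to the last exhalation of methacholine solution".
- **Companion endpoint.** In Protocol 7.3.2 the area "will be calculated from time 0 to tz using the trapezoidal rule", and tz is tied to the post-diluent value.
- **Interpretation.** Protocol 7.3.2 and SAP 7.5 state: "A hazard ratio of greater than one means that BI 443651 is not inferior to placebo".

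The Cox model adjusts for period and for one baseline value per subject, the median of the period baselines. The PHREG code in SAP 9.2.1 takes the analysis time and the censoring flag as supplied, so it settles neither the origin nor the reference.

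**The concern.** The nadir comes after treatment and may depend on it. Any delay to the nadir is subtracted from the recorded recovery time, so two challenges can be ranked in the wrong order on the scale that matters to a subject, time since methacholine. That Cox regression uses only ranks is no protection, because a subject-specific origin changes the ranks. The baseline covariate is none either: a single median per subject cannot remove a shift that occurs under one treatment.

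The direction matters because the trial looks for harm. A shorter recorded time on BI 443651 moves the hazard ratio above 1, the side the plan reads as reassuring. Separately, the reference wording leaves two possible recovery thresholds, and the stop rule shortens recorded times, including those in the Kaplan-Meier plots.

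**Working it through.** The plan gives no event count, power or expected value for this endpoint, so there is no figure to reproduce. The check applies the written rule to the Day 2 schedule in note 18: 0.5, 1.5, 5, 10, 20, 30, 45 and 60 min, then every 15 min to 3 h, ending "3.0, 3.5, 4.0, 4.5, 5.0, 6.0, 7.0 and 8.0 hours" (23 readings).

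**1. Order of recovery.** Written rule: recorded time = last unrecovered reading − nadir time.

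- Challenge A: nadir 1.5 min, last unrecovered 30 min, first recovered 45 min.
- Challenge B: nadir 20 min, last unrecovered 45 min, first recovered 60 min.

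| Clock | A (min) | B (min) | Order |
|---|---|---|---|
| Nadir to last unrecovered (as written) | 30 − 1.5 = 28.5 | 45 − 20 = 25 | reversed |
| Nadir to first recovered | 45 − 1.5 = 43.5 | 60 − 20 = 40 | reversed |
| Time 0 to last unrecovered | 30 | 45 | correct |
| Time 0 to first recovered | 45 | 60 | correct |

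B recovers 15 min later but scores 3.5 min shorter. In general the order reverses when the nadir is later by more than the last unrecovered reading is; here 18.5 min > 15 min. With B's nadir also at 1.5 min, B scores 43.5 min and the order is right.

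**2. All schedule patterns.** Take every pair of challenges with the nadir at or before 30 min in which one recovers later than the other: 6511 pairs.

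| Clock | Reversed | Tied |
|---|---|---|
| Nadir to last unrecovered | 85 | 27 |
| Nadir to first recovered | 65 | 12 |
| Time 0 to last unrecovered | 0 | 0 |
| Time 0 to first recovered | 0 | 0 |

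These count possible patterns; they are not probabilities. They show that the nadir start is what reverses order.

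**3. Stop rule.** The recorded stop precedes the first recovered reading by 15 min for recoveries first seen from 45 min to 3 h, 30 min for those after 3 h up to 5 h, and 60 min for those after 5 h up to 8 h. True recovery lies somewhere between the two readings, so these are upper limits on the shortening. If the nadir is itself the last unrecovered reading, the recorded time is 0.

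**4. Reference (assumed values).** Let FEV₁(t) = post-diluent × (1 − 0.25 × exp(−t/60)), t in minutes, with a pre-challenge value of 3.00 L. The pre-challenge threshold is 0.95 × 3.00 = 2.850 L. Recovery against the post-diluent threshold is first seen at 105 min in every row.

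| Post-diluent (L) | Post-diluent threshold (L) | First reading at or above 2.850 L |
|---|---|---|
| 3.06 | 2.907 | 90 min |
| 3.00 | 2.850 | 105 min |
| 2.94 | 2.793 | 135 min |
| 2.85 | 2.708 | not by 8 h |

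**5. Effect on the hazard ratio (illustration on assumed curves).** Two independent arms of 4000, Breslow ties, 25% fall, median nadir 2 min and median recovery 105 min on placebo, measurement noise of 0 or 2% of post-diluent. True recovery on active is 10 min later throughout.

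| Nadir delay on active | HR, written rule | HR, time 0 to first recovered reading after the nadir |
|---|---|---|
| 0 min | 0.79 to 0.82 | 0.80 to 0.83 |
| 10 min | 1.05 to 1.14 | 0.80 to 0.82 |
| 20 min | 1.18 to 1.24 | 0.79 to 0.80 |
| 30 min | 1.29 to 1.33 | 0.76 to 0.81 |

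With no delay the two clocks agree. With a delay, the written rule moves a slower recovery to the other side of 1.

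**The case against.** **A nadir start can be defended.** Protocol 5.7 separates the induced bronchoconstriction from the recovery that follows, and nadir-to-recovery isolates the second. Depth is the primary endpoint, and a longer obstruction would extend tz and tend to show in the AUC. This stands as a reason to keep the quantity as a description. It does not stand as a reason for the present label and hazard-ratio reading: the documents neither state nor justify that estimand.

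**Nothing in the documents says the nadir is delayed.** Protocol 1.2.1 reports a larger constriction in guinea pigs, and 1.1 a rapid return to baseline with and without drug. This stands. A reader might infer that the drug does delay the nadir and that the hazard ratio will be biased; the documents hold no nadir-timing data and do not support that.

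**The stop rule is a convention.** It matches tz and applies to every arm. A reader might infer that it makes each time a full interval too short, or that it reverses order too. Neither follows: the shortening is at most one interval, a first-recovered stop is late by up to the same amount, and from time 0 the stop rule produced no reversals.

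**The reference may be loose wording.** The defining sentence itself opens with the post-diluent value, and the last reading before methacholine could loosely be called pre-challenge. That is the likelier intent, but note 18 lists two readings and the SAP does not reconcile them.

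Figure 5.1:1 and the internal standard 001-MCG-163 were not available and might clarify the intent.

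**Conclusion.** The concern holds in limited form. The reference in the definition contradicts the endpoint's name, the AUC endpoint and the separate readings in note 18; that rests on the text alone. The nadir origin can reverse the order of recovery towards a hazard ratio above 1, as in 28.5 against 25 min for recoveries first seen at 45 and 60 min. This requires a treatment that delays the nadir, and its frequency is unknown. The hazard ratios above are illustrations on assumed curves. The stop rule is a lesser matter: up to 15, 30 or 60 min of shortening depending on the time of recovery, and possible zeros.

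A reader might go further and conclude that the trial's safety assessment is undermined. The documents do not support that: this is one secondary endpoint in a trial with no confirmatory test (Protocol 7.2), alongside depth and AUC. It should still be corrected, because the possible error lies in the reassuring direction.

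**What to change.** In SAP 7.5, recorded as a change in SAP section 4:

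- Measure from the last exhalation of methacholine to the first scheduled reading after the maximum reduction with FEV₁ at or above 95% of the post-diluent value. The condition that the reading follows the maximum reduction is essential: without it, an FEV₁ still at or above 95% at 30 s, before the fall, would count as recovery.
- Censor at the last reading if recovery is not seen. SAP 7.5 states a non-recovery rule only for the AUC.
- State one rule, the same for all treatments, for challenges in which FEV₁ never falls below 95% of post-diluent. SAP 7.5 covers that case only for the AUC.
- Refer to the post-diluent value throughout, and use the same derivation at baseline and treatment challenges. The baseline schedule ends at 3 h and Day 2 at 8 h, so say what an unrecovered baseline contributes to the covariate.
- Nadir-to-recovery time may be kept as a supportive description under its own name.

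The cost is SAP wording and one changed derivation. No new data are needed.

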7. STATISTICAL METHODS AND DETERMINATION OF SAMPLE SIZE

7.1 STATISTICAL DESIGN – MODEL

The primary objective of the study is to investigate safety and tolerability of three consecutive administrations, 12 h apart, at three different dose-levels (100, 400 and 1200 µg) of BI 443651 administered via oral inhalation in male and female mild asthmatic subjects after a bolus MCh challenge.

For the main part, the primary endpoint absolute change in maximum reduction of FEV₁ and the secondary endpoint relative change in AUC_{0-tz} as described in [Section 5.1](#) will be analysed using a mixed effects model on the original and logarithmic-scale, respectively, taking the crossover design of the trial into account. The models will include treatment and period as fixed effects, subject as a random effect and period baseline as well as subject baseline as covariates. The subject baseline will be obtained by calculating the mean of period baselines for each subject. Active doses will be compared to placebo for both endpoints. For investigation of the secondary endpoint time to recovery to within 95% of post-diluent value a Cox proportional hazards model will be used to estimate the hazard ratio of BI 443651 vs. Placebo.

For the pilot part, the primary and secondary endpoints as described in [Section 5.1](#) will be analysed using descriptive statistics. No inferential statistics are planned for this part of the trial.

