7.7 DETERMINATION OF SAMPLE SIZE

For the pilot part, it is planned to include 4 otherwise healthy asthma subjects. The planned sample size is not based on a power calculation. This sample size is considered as sufficient for the exploratory evaluation of safety after multiple doses in this study population.

For the main part, it is planned to include a total of 32 (8 per sequence) completed otherwise healthy asthma subjects (non-completed subjects will be replaced, see Section 3.3.5) to achieve the aims of this exploratory trial with the following assumptions:

- The primary endpoint is normally distributed
- Two-sided significance level $\alpha = 10\%$
- Considered relevant change: -0.2 L
- The treatment difference between the means of BI 443651 and placebo is expected to be -0.06 L [data on file]
- The within-subject standard deviation (SD) for the difference is expected to be 0.24 L [data on file]

Assuming a within-subject SD of 0.24 L for BI 443651 and given the chosen sample size of N=32 subjects, the precision of the two-sided 90% confidence interval of the difference will be approximately 0.112 (upper confidence limit (UL) – point estimate of the difference (Diff)); for a greater within-subject SD of 0.3, the precision would still be approximately 0.14.

Increasing the sample size by 4 (N=36) results in a precision of approximately 0.105 and 0.131, respectively. [Table 7.7: 1](#) provides an overview of the 90% confidence intervals that are expected with 95% tolerance probability, for possible scenarios of the SDs and intra-subject differences (active drug – placebo).

Proprietary confidential information © 2017 Boehringer Ingelheim International GmbH or one or more of its affiliated companies

Table 7.7: 1 Precision that can be expected with 95% tolerance probability and illustrative two-sided 90% confidence intervals around the treatment differences for different SDs and varying sample sizes in a 4x4x4 crossover

N	SD within	Precision (UL-Diff)	Diff (active – placebo)				
			-0.1	-0.05	0	0.05	0.1
32	0.24	0.112	(-0.21, 0.01)	(-0.16, 0.06)	(-0.11, 0.11)	(-0.06, 0.16)	(-0.01, 0.21)
32	0.3	0.14	(-0.24, 0.04)	(-0.19, 0.09)	(-0.14, 0.14)	(-0.09, 0.19)	(-0.04, 0.24)
36	0.24	0.105	(-0.20, 0.00)	(-0.15, 0.05)	(-0.10, 0.10)	(-0.05, 0.05)	(-0.00, 0.20)
36	0.3	0.131	(-0.23, 0.03)	(-0.18, 0.08)	(-0.13, 0.13)	(-0.08, 0.18)	(-0.03, 0.23)

The calculation was performed as described by Julius [R11-5230] using R Version 3.2.2.

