9.2.1 Details for primary analyses

The following SAS code can be used to fit the model for the primary endpoint:

```
PROC MIXED data=indata METHOD=reml ORDER=formatted;
  CLASS SUBJID ATRTSL APERIOD;
  MODEL CHG = ATRTSL APERIOD BASE baseavg / SOLUTION DDFM = KR
    OUTP=pred;
  RANDOM INTERCEPT / SUBJECT = SUBJID TYPE=VC;
  LSMEANS ATRTSL / PDIFF=control('Placebo') CL ALPHA=0.1;
RUN ;
```

The following SAS code can be used to fit the model for the secondary endpoint 'FEV₁ AUC0-tz':

```
PROC MIXED data= indata METHOD=reml ORDER=formatted ;
  CLASS SUBJID ATRTSL APERIOD;
  MODEL LNRATIO = ATRTSL APERIOD lnbase lnbaseavg / SOLUTION DDFM
    = KR OUTP=pred;
  RANDOM INTERCEPT / SUBJECT = SUBJID TYPE=VC;
  LSMEANS ATRTSL / PDIFF=control('Placebo') CL ALPHA=0.1;
RUN ;
```

The following SAS code can be used to fit the model for the secondary endpoint 'Time to recovery':

```
PROC PHREG DATA= adtte;
  CLASS ATRTSL (REF='Placebo') APERIOD;
  MODEL aval*cnsr(1) = ATRTSL APERIOD BASEAVG / TIES=BRESLOW;
  HAZARDRATIO ATRTSL / DIFF=REF CL=WALD ALPHA=0.05;
  ODS OUTPUT HAZARDRATIOS=hazard;
RUN;
```

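### The Cox model for time to recovery uses a subject-level median baseline and leaves out the period's own baseline recovery time, which the trial collects and the other two models use

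*Protocol*

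**What the plan says.** Protocol 7.3.2 takes the Day 2 time as the endpoint and gives the pre-dose challenge this role: "the time obtained from the baseline challenge will be used for the baseline correction in the analysis". It then defines the only baseline covariate: "Thereby, the subject baseline is calculated as median of all period baselines per subject". The third term in the hazard function "represents the period", which is a period effect and not a period baseline. SAP 7.5 repeats the model, and SAP 9.2.1 codes it as "MODEL aval*cnsr(1) = ATRTSL APERIOD BASEAVG / TIES=BRESLOW".

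The two mixed models are built differently. For them Protocol 7.1 specifies "subject as a random effect and period baseline as well as subject baseline as covariates". The SAP code for the primary endpoint is "MODEL CHG = ATRTSL APERIOD BASE baseavg / SOLUTION DDFM = KR", and the AUC code has the logged equivalents of both baseline terms. Neither document gives a reason for the difference, and SAP section 4 lists no change that bears on it.

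**The concern.** A 3-hour baseline challenge is run before dosing in every period, so each Day 2 recovery time has its own matched baseline. The Cox model reduces the four baselines of a subject to one number that is the same in all four records. That number can separate fast from slow recoverers. It cannot show that a subject's airways were more or less reactive in one period than in another.

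The trial looks for worsened methacholine response, and slower recovery is part of that. In a Cox model, unexplained variation in prognosis moves the estimated hazard ratio towards 1 even when it is balanced across treatments. On a safety endpoint, that is the direction that makes a delay look smaller.

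**Working it through.** **Plan's own figure.** The documents give no hazard ratio, event count or variance for this endpoint. The precision figures in Protocol 7.7 concern the primary endpoint. The first one reproduces, with df = 3(32−1)−3 = 90: 1.662 × 0.24 × √(2/32) = 0.0997, times √(113.1/90) = 1.121, gives 0.112. It has no bearing on the Cox model.

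**Inputs from the documents.** For the main part "it is planned to include a total of 32 (8 per sequence) completed otherwise healthy asthma subjects", so 32 × 4 = 128 records. Sequences are those of Protocol Table 3.1:2. Readings end at 3 h at baseline and 8 h on Day 2 (Protocol 6.2). Ties follow Breslow.

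**Inputs that are assumptions.** All variances, effect sizes and the median recovery time.

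**Step 1: what the extra covariate can explain.** Write log recovery time as a subject effect, plus a period effect u shared by the two challenges of a period, plus challenge noise e with SD 0.4. With the subject level treated as known, the Day 2 residual variance is σu² + σe² without the period baseline and σu²σe²/(σu² + σe²) + σe² with it.
- σu = 0: 0.16 and 0.16, no change.
- σu = 0.3: 0.09 + 0.16 = 0.25, and 0.0144/0.25 + 0.16 = 0.218. SD ratio √(0.25/0.218) = 1.07.
- σu = 0.5: 0.25 + 0.16 = 0.41, and 0.04/0.41 + 0.16 = 0.258. SD ratio √(0.41/0.258) = 1.26.

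As a rough guide, the log hazard ratio for a fixed shift in log time grows with this ratio. The gain should therefore be small at 0.3 and visible at 0.5.

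**Step 2: simulation set A.** Protocol spirometry grid, between-subject SD 0.6, per-challenge SD 0.4, median recovery 1 h, top dose lengthening recovery 1.49-fold, baseline on the raw time scale.

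| Shared period SD | HR, planned | HR, with period baseline | 95% CI excludes 1 |
|---|---|---|---|
| 0 | 0.465 | 0.464 | 84% to 86% |
| 0.3 | 0.518 | 0.501 | 73% to 78% |
| 0.5 | 0.556 | 0.490 | 64% to 77% |

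The shifts are 0.001, 0.017 and 0.066. The log HR ratios, ln 0.501/ln 0.518 = 1.05 and ln 0.490/ln 0.556 = 1.21, are close to step 1. A second run with the same SDs and effect (300 trials per scenario) gave 0.41 to 0.41, 0.45 to 0.43 and 0.53 to 0.48.

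**Step 3: simulation set B.** Same design and grid, conditional HR 0.5, Weibull recovery times with median 1 h, normal effects on the log hazard, 400 trials per scenario. Each shift is the planned HR minus the HR in the column before it.

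| Shape | Subject variance | Subject-by-period variance | Planned | With period baseline | Shift | Stratified by subject only | Shift |
|---|---|---|---|---|---|---|---|
| 1.5 | 1 | 0 | 0.577 | 0.573 | 0.004 | 0.512 | 0.065 |
| 1.5 | 1 | 0.25 | 0.599 | 0.594 | 0.005 | 0.553 | 0.046 |
| 1.5 | 2 | 0.5 | 0.617 | 0.605 | 0.012 | 0.582 | 0.035 |
| 1.5 | 1 | 1 | 0.648 | 0.635 | 0.013 | 0.614 | 0.034 |
| 1.5 | 2 | 2 | 0.714 | 0.655 | 0.059 | 0.691 | 0.023 |
| 3 | 1 | 0 | 0.616 | 0.612 | 0.004 | 0.565 | 0.051 |
| 3 | 1 | 0.25 | 0.634 | 0.624 | 0.010 | 0.595 | 0.039 |
| 3 | 2 | 0.5 | 0.657 | 0.645 | 0.012 | 0.617 | 0.040 |
| 3 | 1 | 1 | 0.660 | 0.634 | 0.026 | 0.632 | 0.028 |
| 3 | 2 | 2 | 0.696 | 0.647 | 0.049 | 0.681 | 0.015 |

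The period baseline moves the HR away from 1 in all ten scenarios. Stratifying by subject removes more in eight of ten; the exceptions are the two rows with both variances at 2. The share of 95% intervals excluding 1 changes by between −2 points (46% to 44%) and +13 points (26% to 39%). The Monte Carlo error of one such share is about √(0.25/400) = 2.5 points.

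**The case against.** The specification is coherent as written. The sentence on baseline correction does not promise a correction period by period. The same section then defines the correction as the subject median, and the SAP implements exactly that. A reader might infer that protocol and model contradict each other; the text does not support that. Nor is the baseline data ignored, since every period baseline feeds the median and a period effect is in the model.

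A reader might also infer that a within-subject hazard ratio is being diluted and that this covariate would restore it. The model has no strata, frailty or other subject term, so it does not estimate a within-subject hazard ratio, and in set B the estimate stays well above 0.5 after the addition. Nor is confounding at issue, because the Williams design balances period baselines across treatments in expectation.

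The stakes are limited. The endpoint is secondary and Protocol 7.2 plans no confirmatory test. The "asymptotic 95% Wald confidence intervals will be estimated" as interval estimates, so the share of intervals excluding 1 describes precision and is not a planned decision rule. The AUC endpoint also responds to slow recovery and already adjusts for period baseline.

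All of this stands. What remains is that a matched covariate, used in the two other models, is left out of this one without a stated reason. Handling the subject term would not replace it: adding the period baseline to the stratified model still moved the HR from 0.691 to 0.611 and from 0.681 to 0.614 in the two high-variance rows.

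**Conclusion.** The point holds as an improvement to an exploratory secondary analysis. The omission is plain in both documents. Its direction is known if recovery varies from period to period in a way that both challenges share: the hazard ratio sits somewhat closer to 1 than it need. Its size cannot be derived from the documents. Under the assumptions above, the shift is 0.00 with no shared variation, about 0.01 to 0.03 with moderate variation, and about 0.05 to 0.07 when shared variation is as large as the largest values tried. Without shared variation the addition costs practically nothing. The missing subject term is a separate matter and usually the larger source of attenuation.

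**What to change.** In Protocol 7.3.2, SAP 7.5 and the PHREG step in SAP 9.2.1, add the period baseline so that the right-hand side reads `ATRTSL APERIOD BASE BASEAVG`. BASE is that period's baseline recovery time and BASEAVG stays the subject median. State these rules with it:

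- Scale: raw time, or log with a stated offset. The clock starts at the lowest FEV1, so the time is zero when that reading is also the last one before recovery, and a plain log would lose the record.
- Baseline not recovered by the last reading at 3 h: enter the time from the lowest FEV1 to that last reading. A flat 3 h would not match the clock.
- Baseline challenge with no fall below 95% of the post-diluent value: enter zero. SAP 7.5 covers this case for the AUC only.
- Compute the median from values set by the same rules, and record the change in SAP section 4.

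The cost is SAP wording and one degree of freedom: eight coefficients (3 treatment, 3 period, 2 baseline) instead of seven, on up to 128 records. No new data are needed.
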